4.0 PATIENT SELECTION

This study can fulfill its objectives only if appropriate patients are enrolled. The following eligibility criteria are designed to select patients for whom protocol treatment is considered appropriate. All relevant medical and non- medical conditions should be taken into consideration when deciding whether this protocol is suitable for a particular patient.

Patient eligibility should be reviewed and documented by an appropriately qualified member of the investigator's study team before patients are included in the study. Patients must meet all of the following inclusion criteria and none of the exclusion criteria to be eligible for enrollment into the study:

The baseline tumor assessment must have taken place within 28 days prior to start of treatment. Under no circumstances are patients, who were once enrolled and treated in this study, permitted to be re-enrolled into the same study. If patients screenfail prior to receiving treatment, the patient may be re-enrolled if eligible.

4.1 Inclusion Criteria

To be eligible for this trial, subjects must fulfill the following criteria:

1. Subjects must be refractory to, or intolerant of, established therapy known to provide clinical benefit for their conditions, or where subjects refuse existing therapies.
2. Subjects must have measurable disease (RECIST v1.1) or patients may have bone metastatic disease evaluable by Prostate Cancer Working Group 2 (PCWG2) for subjects with metastatic castration-resistant prostate cancer (CRPC) or according to tumor evaluation criteria best suitable and accepted for the tumor type evaluated.
3. Age \geq 18 years.
4. Eastern Cooperative Oncology Group (ECOG) performance status of 0-1.
5. Adequate hematologic function defined as:

- Platelets $\geq 100 \times 10^9/L$ (For patients with hepatocellular carcinoma, Platelets $\geq 70 \times 10^9/L$);
- Hemoglobin $\geq 9 \text{ g/dL}$;
- Absolute Neutrophil Count (ANC) $\geq 1.5 \times 10^9/L$;
- White Blood Cell (WBC) $\geq 3 \times 10^9/L$.

6. Adequate liver function defined as:

- Alanine transaminase (ALT) $\leq 2.5 \times$ upper normal limit (ULN) ($\leq 5 \times$ ULN for subjects with documented metastatic disease to the liver);
- Aspartate aminotransferase (AST) $\leq 2.5 \times$ ULN ($\leq 5 \times$ ULN for subjects with documented metastatic disease to the liver);
- Alkaline phosphatase $< 4 \times$ ULN;
- Total Bilirubin $\leq 1.5 \times$ ULN (In the expansion cohort, subjects with Gilbert's syndrome [hereditary indirect hyperbilirubinemia] who must have a total bilirubin of $\leq 3 \times$ ULN);
- Albumin $\geq 3 \text{ g/dL}$.

7. Renal function defined serum creatinine $\leq 2 \times$ upper limit of normal (ULN) or estimated creatinine clearance $\geq 30 \text{ ml/min}$ as calculated using the Cockcroft-Gault formula.

8. Subject has recovered to Grade ≤ 1 by the National Cancer Institute Common Terminology Criteria for Adverse Events, Version 4.03 (NCI-CTCAE v4.03)¹⁴ from the effects of recent surgery, radiotherapy, chemotherapy, hormonal therapy, or other targeted therapies, with the exception of alopecia. The exceptions for such effects are allowed lab values of \leq Grade 2 specified elsewhere in these inclusion criteria.

9. Life expectancy of at least 12 weeks.

10. Negative serum pregnancy test in women of childbearing potential within 7 days of first dose of treatment and patients of child-bearing potential must agree to use effective contraception during and after 90 days post dose. A woman of childbearing potential is defined as a premenopausal female capable of becoming pregnant. This includes women on oral, injectable or mechanical contraception; women who are single and women whose male sexual partners have been vasectomized or whose male sexual partners have received or are utilizing mechanical contraceptive devices.

11. Subjects must have biopsiable disease. For Arms A, B, and C, subjects must have at least two lesions amenable to biopsy and response evaluation. For Arm D subjects should have at least three lesions amenable to biopsy, response evaluation, and radiation. Tumor lesions used for biopsy should not be lesions used as RECIST target lesions. However, if patients in Arm D do not have three separate lesions, patients will be eligible if there are two lesions, in which one is > 2 centimeters (short axis) and can be used for both biopsy and response evaluation.
12. Subjects must give informed consent according to the rules and regulations of the individual participating sites.

4.2 Exclusion Criteria

Subjects with any of the following will not be eligible for the study:

1. Subjects with primary central nervous system (CNS) tumor or CNS tumor involvement. However, subjects with metastatic CNS tumors may participate in this study if the subject is:
 - >4 weeks from prior therapy completion (including radiation and/or surgery)
 - Clinically stable with respect to the CNS tumor at the time of study entry
 - Not receiving steroid therapy in treating CNS tumor or CNS tumor involvement
 - Not receiving anti-convulsive medications (that were started for brain metastases).
2. Major surgery, radiation therapy or systemic anti-cancer therapy within 4 weeks of study drug administration (6 weeks for mitomycin C or nitrosoureas). Palliative radiotherapy to a limited field is allowed after consultation with the medical monitor at any time during study participation, including during screening, unless it's clearly indicative of disease progression.
3. Subjects with prior anti-PD-1, anti-PD-L1 treatment. For Arms A and D, subjects may not have had prior 4-1BB treatment. For Arm B, subjects may not have had prior OX40 treatment. For Arm C, subjects may not have had prior 4-1BB or OX40 treatment.

4. Diagnosis or recurrence of invasive cancer other than the present cancer within 3 years (except basal or squamous cell carcinoma of the skin that has been definitively treated).
5. Clinically significant (i.e., active) cardiovascular disease: cerebral vascular accident/stroke (< 6 months prior to enrollment), myocardial infarction (< 6 months prior to enrollment), unstable angina, congestive heart failure (>/= New York Heart Association Classification Class II), or serious cardiac arrhythmia requiring medication.
6. Active infection requiring systemic therapy.
7. Treatment with an investigational anti-cancer study drug within 4 weeks prior to study drug administration date.
8. Concurrent therapy with approved or investigational anticancer therapeutics.
9. Known prior severe hypersensitivity to investigational product(s) or any component in its formulations, including known severe hypersensitivity reactions to monoclonal antibodies (NCI CTCAE v4.03 Grade >/= 3).
10. Current use of immunosuppressive medication, EXCEPT for the following: a. intranasal, inhaled, topical steroids, or local steroid injection (e.g., intra-articular injection); b. Systemic corticosteroids at physiologic doses </= 10 mg/day of prednisone or equivalent; c. Steroids as premedication for hypersensitivity reactions (e.g., CT scan premedication).
11. Active autoimmune disease that might deteriorate when receiving an immuno-stimulatory agent. Patients with diabetes type I, vitiligo, psoriasis, or hypo- or hyperthyroid diseases not requiring immunosuppressive treatment are eligible.
12. Prior organ transplantation including allogenic stem-cell transplantation.
13. Known history of testing positive for HIV or known acquired immunodeficiency syndrome.
14. Hepatitis B virus (HBV) or hepatitis C virus (HCV) infection at screening (positive HBV surface antigen or HCV RNA if anti-HCV antibody screening test positive)
15. Vaccination (live attenuated virus) within 4 weeks of the first dose of avelumab and while on trials is prohibited except for administration of inactivated vaccines.

16. Persisting toxicity related to prior therapy (NCI CTCAE v. 4.03 Grade > 1); however, alopecia, sensory neuropathy Grade </= 2, or other Grade </= 2 not constituting a safety risk based on investigator's judgment are acceptable.
17. Other severe acute or chronic medical conditions including colitis, inflammatory bowel disease, pneumonitis, pulmonary fibrosis or psychiatric conditions including recent (within the past year) or active suicidal ideation or behavior; or laboratory abnormalities that may increase the risk associated with study participation or study treatment administration or may interfere with the interpretation of study results and, in the judgment of the investigator, would make the patient inappropriate for entry into this study.
18. Medical, psychological or social conditions that may interfere with the patient's participation in the study or evaluation of the study results.
19. Pregnancy or lactation.
20. Men whose partner is a woman of child-bearing potential, (i.e. biologically able to conceive), and who is not employing two forms of highly effective contraception. Highly effective contraception (e.g. male condom with spermicide, diaphragm with spermicide, intra-uterine device) must be used by both sexes during the study and must be continued for 90 days after the end of study treatment. Women of child-bearing potential is defined as sexually mature women who are not surgically sterile or who have not been naturally postmenopausal for at least 12 consecutive months (e.g., who has had menses any time in the preceding 12 consecutive months).
21. A diagnosis of active scleroderma, lupus, or other rheumatologic disease which in the opinion of the treating radiation oncologist precludes safe radiation therapy.
22. Has had prior radiation therapy within the past 3 months where the high dose area of the prior radiation would overlap with the high dose area of the intended radiation based on the judgement of the treatment oncologist.

4.3 Pregnancy and Contraception

In this study, patients of childbearing potential will receive study drug(s), for which the teratogenic risks are currently unknown. Patients should not become pregnant or father a child while on this study because the drugs in this study can affect an unborn baby. Women should not breastfeed a baby while on this study. It is important patients understand the need to use birth control while on this study. Female patients of childbearing potential must have a negative serum pregnancy test at screening and agree to use reliable methods of contraception for 90 days after their last dose of medication.

Two (2) methods of highly effective contraception must be used throughout the study and continued for at least 90 days after the last dose. The investigator, in consultation with the patient, will select two appropriate methods of contraception for the individual patient from the permitted list of contraception methods, and instruct the patient in their consistent and correct use. The investigator, at each study visit, will discuss with the patient the need to use highly effective contraception consistently and correctly and document such conversation in the patient chart. In addition, the investigator will instruct the patient to call immediately if a selected birth control method is discontinued or if pregnancy is known or suspected.

Highly effective methods of contraception are those that, alone or in combination, result in a failure rate of less than 1% per year when used consistently and correctly (ie, perfect use) and include:

1. Established use of oral, inserted, injected or implanted hormonal methods of contraception are allowed provided the patient remains on the same treatment throughout the entire study and has been using that hormonal contraceptive for an adequate period of time to ensure effectiveness.
2. Correctly placed copper containing intrauterine device (IUD).
3. Male condom or female condom used WITH a spermicide (ie, foam, gel, film, cream, suppository).
4. Male sterilization with appropriately confirmed absence of sperm in the post-vasectomy ejaculate.
5. Bilateral tubal ligation or bilateral salpingectomy.

5.0 STUDY TREATMENTS

5.1 Allocation to Treatment

Eligible patients will be enrolled to receive one of the study drug combinations in an open-labeled, unblinded manner. Patients will be registered and successively assigned to the next available treatment slot at a dose level decided on after the previous cohort's safety evaluation and ongoing observations of earlier enrolled patients.

Dose level allocation will be performed after patients have given their written informed consent and have completed the necessary baseline assessments.

5.2 Investigational Product Supplies

Avelumab, utomilumab (4-1BB), and PF-04518600 (OX40) will be supplied for the study by Pfizer.

The Investigational Pharmacy will receive a supply of study drug(s) prior to activation with instructions on how to confirm drug receipt. Resupplies will be made during the course of the study based on need.

5.2.1 Formulation and Packaging

5.2.1.1 Avelumab

The active pharmaceutical ingredient in avelumab drug product is a fully human antibody (calculated molecular weight of 143832 Dalton) of the immunoglobulin G (IgG) 1 isotype that specifically targets and blocks PD-L1, the ligand for PD-1.

Avelumab drug product is a sterile, clear, and colorless concentrate for solution intended for intravenous (IV) infusion. The drug is presented at a concentration of 20 mg/mL in single-use glass vial containing 200 mg of avelumab.

Avelumab drug product must be stored at 2°C to 8°C until use, and it must not be frozen. Rough shaking of avelumab product must be avoided. Avelumab drug product must be diluted with 0.9% saline solution; alternatively a 0.45% saline solution can be used if needed. It is recommended that the diluted avelumab solution is used immediately.

5.2.1.2 *Utomilumab (4-1BB)*

Utomilumab is provided as a 10 mg/mL sterile solution for injection, in a 20 mM histidine buffered solution at pH 5.5. The drug product is supplied in 2 mL Type 1 clear glass vial sealed with a coated serum stopper and aluminum seal (nominal fill volume of 2.0 mL or 10.0 mL). The labeled storage conditions for utomilumab, Injection, 10 mg/mL is 2–8°C, and it should not be frozen.

5.2.1.3 *PF-04518600 (OX40)*

PF-04518600 drug product, 10 mg/mL is presented as an aqueous solution compounded in histidine buffer with excipients at pH 5.5. The drug product is supplied in sterilized 10 mL Type 1 clear glass vials with 20 mm serum stoppers and 20 mm aluminum flip-off seals, with a nominal fill volume of 10 mL. The drug product should be stored refrigerated (2-8 °C) and protected from light.

5.2.2 Preparation and Dispensing

5.2.2.1 *Avelumab*

For administration in clinical trials, avelumab drug product must be diluted with 0.9% saline solution (sodium chloride injection) supplied in an infusion bag; alternatively a 0.45% saline solution can be used if needed. Detailed information on infusion bags and medical devices to be used for the preparation of the dilutions and subsequent administration will be provided in the manual of preparation.

To prepare the dilutions, subsequent preparation steps must be accomplished by adequate trained personnel under a laminar flow box using aseptic techniques.

Prior to the preparation of the dilution for final infusion, allow each vial to equilibrate to room temperature. Use a disposable syringe equipped with a needle of suitable size

to remove a volume of sodium chloride solution to be replaced by avelumab from the infusion bag and discard the removed solution. Use a new disposable syringe equipped with a needle of suitable size to inject a volume of avelumab drug product identical to the discarded volume of sodium chloride solution into the infusion bag. Gently invert the mixture 10 times. Infusion bags must not be shaken, in order to avoid foaming or excessive shearing of the protein solution. The preparation must be carefully inspected as it should result in a homogeneous looking clear solution, free of visible particles.

5.2.1.2 *Utomilumab (4-1BB)*

Refrigerated utomilumab drug product will be equilibrated to ambient temperature before preparation and administration.

5.2.1.3 *PF-04518600 (OX40)*

PF-04518600 10 mg/mL injection is presented as a sterile solution for intravenous administration. Each vial has a nominal volume of 10 mL, is sealed with a coated stopper and an overseal, and labeled according to local regulatory requirements. The vial is intended for single use only.

PF-04518600 will be shipped under refrigerated conditions (2-8°C) that are monitored with temperature control monitoring devices.

5.2.3 Administration, Dose Calculation and Infusion Reactions

5.2.3.1 *Avelumab*

Avelumab will be administered as a 1-hour (+/- 30 minutes) infusion dose of 10 mg/kg body weight administered IV once every 2 weeks starting on Cycle 1 Day 15.

Subjects are at risk of developing infusion-related reactions including drug hypersensitivity reactions, mainly mild to moderate, but which may also be life-threatening. Premedication with an antihistamine and with paracetamol (acetaminophen) (e.g., 25-50 mg diphenhydramine and 500-650 mg paracetamol [acetaminophen] IV or oral equivalent) is mandatory prior to each dose of avelumab.

Avelumab should be administered in a setting that allows for immediate access to an intensive care unit or equivalent environment and administration of therapy for anaphylaxis, such as the ability to implement immediate resuscitation measures. Steroids (dexamethasone 10 mg), epinephrine (1:1,000 dilution), allergy medications (IV antihistamines), bronchodilators, or equivalents, and oxygen should be available for immediate access.

Following avelumab infusions, patients must be observed for 2 hours post-infusion for potential infusion-related reactions

5.2.3.2 *Utomilumab (4-1BB)*

Patients will receive doses of utomilumab IV once every four weeks (one cycle). A cycle is defined as the time from day 1 dose to the next day 1 dose. If there are no treatment delays, a cycle will be four weeks in duration.

Pre-medication is recommended for all patients, and may include an antihistamine, anti-inflammatory agent or pain reliever.

The duration of infusion is 1 hour (+/- 30 minutes). The infusion rate should be reduced or interrupted in the case of symptoms of infusion reaction, and symptomatic treatment administered. The infusion may be continued at one-half the previous rate upon improvement of symptoms. If symptoms persist or worsen, the infusion should be discontinued.

5.2.3.3 *PF-04518600 (OX40)*

PF-04518600 will be administered as an intravenous infusion over 1 hour (+/- 5 minutes) on Days 1 and 15 of each 28-day cycle. In previous studies, the starting dose for the monotherapy portion of the study was 0.01 mg/kg IV with escalation to subsequent dosages of 0.1, 0.3, 1.5, and 3.0 mg/kg after review of the results. The starting dose for PF-04518600 in combination with utomilumab will be 0.1 mg/kg, escalating to 0.3 mg/kg. On cycles whereby both PF-04518600 and utomilumab are to be administered on the same day, PF-04518600 will be administered after, but no

sooner than 30 minutes after completion of the utomilumab infusion in absence of infusion reaction.

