Adverse events (both non-serious and serious) associated with study drug(s) exposure may represent an immunologic etiology. These adverse events may occur shortly after the first dose or several months after the last dose of treatment. Immunotherapy study drugs (avelumab, utomilumab, and PF-04518600) must be withheld for drug-related toxicities and severe or life-threatening AEs as per Table 8-10 below. Where appropriate, these guidelines include the use of oral or intravenous treatment with corticosteroids as well as additional anti-inflammatory agents if symptoms do not improve with administration of corticosteroids. Note that several courses of steroid tapering may be necessary as symptoms may worsen when the steroid dose is decreased. The dose modification guidelines are intended to be applied when the physician determines the events to be related to one or more of the immunotherapy study drugs (avelumab, utomilumab, and PF-04518600).

For subjects whose dose was withheld due to toxicity, subjects may resume immunotherapy study drug(s) (avelumab, utomilumab, and PF-04518600) upon resolution of toxicity to Grade 0-1 or baseline.

Table 8. Adverse Drug Reactions Requiring Immunotherapy Agent Discontinuation or Modification

In the following table, immunotherapy study drugs or agents refer to avelumab, utomilumab, or PF-04518600.

Any Grade 4 Adverse Drug Reactions (ADRs) require treatment discontinuation with immunotherapy agents (avelumab, utomilumab, or PF-04518600) except for single laboratory values out of normal range that are unlikely related to study treatment as assessed by the Investigator, do not have any clinical correlate, and resolve within 7 days with adequate medical management

Any Grade 3 ADRs require treatment discontinuation with immunotherapy agents except for any of the following:

- Transient (\leq 6 hours) Grade 3 flu-like symptoms or fever, which is controlled with medical management
- Transient (\leq 24 hours) Grade 3 fatigue, local reactions, headache, nausea, emesis that resolves to Grade \leq 1
- Single laboratory values out of normal range (excluding Grade \geq 3 liver function test increase) that are unlikely related to study treatment according to the Investigator, do not have any clinical correlate, and resolve to Grade \leq 1 within 7 days with adequate medical management
- Tumor flare phenomenon defined as local pain, irritation, or rash localized at sites of known or suspected tumor

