- Change in ECOG PS to \geq 3 that does not resolve to \leq 2 within 14 days (infusions should not be given on the following cycle, if the ECOG PS is \geq 3 on the day of study drug administration)

Any Grade 2 ADR should be managed as follows:

- If a Grade 2 ADR resolves to Grade \leq 1 by the last day of the current cycle, treatment may continue.
- If a Grade 2 ADR does not resolve to Grade \leq 1 by the last day of the current cycle, infusions should not be given on the following cycle. If at the end of the following cycle the event has not resolved to Grade 1, the subject should permanently discontinue treatment with an **immunotherapy agent** ADR (except for hormone insufficiencies, that can be managed by replacement therapy; for these hormone insufficiencies, up to 2 subsequent doses may be omitted).
- Upon the second occurrence of the same Grade 2 ADR (except for hormone insufficiencies that can be managed by replacement therapy) in the same subject, treatment with **immunotherapy agents** has to be permanently discontinued.

Table 9. Treatment Modification for Symptoms of Infusion-Related Reactions

In the following table, immunotherapy study drugs or agents refer to avelumab, utomilumab, or PF-04518600.

NCI-CTCAE Grade	Treatment Modification for Study Drug
Grade 1 – mild Mild transient reaction; infusion interruption not indicated; intervention not indicated.	Decrease the study drug infusion rate by 50% and monitor closely for any worsening. The total infusion time for study drug should not exceed 120 minutes.
Grade 2 – moderate Therapy or infusion interruption indicated but responds promptly to symptomatic treatment (for example, antihistamines, NSAIDs, narcotics, IV fluids); prophylactic medications indicated for ≤ 24 h.	Stop study drug infusion. Resume infusion at 50% of previous rate once infusion-related reaction has resolved or decreased to at least Grade 1 in severity, and monitor closely for any worsening.

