Grade 3 or Grade 4 – severe or life-threatening Grade 3: Prolonged (for example, not rapidly responsive to symptomatic medication and/or brief interruption of infusion); recurrence of symptoms following initial improvement; hospitalization indicated for clinical sequelae. Grade 4: Life-threatening consequences; urgent intervention indicated.	Stop the study drug infusion immediately and disconnect infusion tubing from the subject. Subjects have to be withdrawn immediately from study drug treatment and must not receive any further study drug treatment.

 - Once the immunotherapy agents infusion rate has been decreased by 50% or interrupted due to an infusion-related reaction, it must remain decreased for all subsequent infusions. - If the subject has a second infusion-related reaction Grade ≥ 2 on the slower infusion rate, the infusion should be stopped and the subject should be removed from study treatment. - If hypersensitivity reaction occurs, the subject must be treated according to the best available medical practice. 	

IV = intravenous; NCI-CTCAE = National Cancer Institute-Common Terminology Criteria for Adverse Event; NSAIDs = nonsteroidal anti-inflammatory drugs.

Table 10. Management of Immune-mediated Adverse Reactions

In the following table, immunotherapy study drugs or agents refer to avelumab, utomilumab, or PF-04518600.

Since inhibition of PD-L1 stimulates the immune system, immune-related AEs (irAEs) may occur.

Treatment of irAEs is mainly dependent upon severity (NCI-CTCAE grade):

Grade 1 to 2: treat symptomatically or with moderate dose steroids, more frequent monitoring

Grade 1 to 2 (persistent): manage similar to high grade AE (Grade 3 to 4)

Grade 3 to 4: treat with high dose corticosteroids

Treatment of gastrointestinal, dermatological, pulmonary, hepatic and endocrine irAEs should follow guidelines set forth in the table.

Gastrointestinal irAEs		
Severity of Diarrhea / Colitis (NCI-CTCAE v4.03)	Management	Follow-up
Grade 1 Diarrhea: < 4 stools/day over Baseline Colitis: asymptomatic	Continue immunotherapy agent therapy Symptomatic treatment (for example, loperamide)	Close monitoring for worsening symptoms Educate subject to report worsening immediately If worsens: Treat as Grade 2 or 3/4

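### Section 5.2.3.2 lets a utomilumab infusion continue at half rate once a reaction improves, without the grade limits that Table 9 imposes on the same drug

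*Combined protocol and SAP*

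**What the plan says.** Section 5.2.3 covers administration, dose calculation and infusion reactions, drug by drug. For utomilumab (Section 5.2.3.2), symptoms of a reaction lead to slowing or interrupting the infusion and treating the symptoms. Two sentences then decide what happens next: "The infusion may be continued at one-half the previous rate upon improvement of symptoms", and "If symptoms persist or worsen, the infusion should be discontinued". Neither carries a CTCAE grade, and neither refers the reader elsewhere.

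Table 9 in Section 5.2.4.3 deals with infusion-related reactions by grade. Its scope is explicit: "In the following table, immunotherapy study drugs or agents refer to avelumab, utomilumab, or PF-04518600". Its rules are:

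- Grade 1: halve the rate and watch closely.
- Grade 2: stop, then "Resume infusion at 50% of previous rate once infusion-related reaction has resolved or decreased to at least Grade 1 in severity".
- Grade 3 or 4: stop, disconnect the tubing, and "Subjects have to be withdrawn immediately from study drug treatment and must not receive any further study drug treatment". The Grade 3 description includes "recurrence of symptoms following initial improvement".
- Second reaction of Grade 2 or worse "on the slower infusion rate, the infusion should be stopped and the subject should be removed from study treatment".

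The text leading into the tables says that the immunotherapy drugs "must be withheld for drug-related toxicities and severe or life-threatening AEs as per Table 8-10 below".

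**The concern.** An infusion reaction is managed in minutes. Staff giving utomilumab would naturally turn to the drug-specific text in a section whose title names infusion reactions. Read alone, that text makes improvement the test for going on. Table 9 makes grade the test, and for Grade 3 or 4 it does not matter whether the reaction improves.

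At stake is same-day re-exposure of a patient whom Table 9 would withdraw, or a restart while a reaction has eased but is still Grade 2. This affects the arms that receive utomilumab: A, C and D. It is a matter of patient safety and consistent conduct, not of inference.

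**Working it through.** The plan gives no figure to reproduce, so the main check sets the two texts side by side.

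| Situation | Section 5.2.3.2 | Table 9 | Result |
|---|---|---|---|
| Grade 1 | Half rate once improved | Half rate, close watch | Compatible |
| First Grade 2 | Half rate once improved | Half rate only once cleared or down to Grade 1 | Same rate, looser threshold in 5.2.3.2 |
| Grade 3, prolonged | Infusion ends, because symptoms persist | Stop and withdraw | Both stop; only Table 9 withdraws |
| Grade 3, needing hospitalization or recurring, that then improves | Half rate permitted as written | Stop and withdraw | Conflict |
| Grade 4 that then improves | Half rate permitted as written | Stop and withdraw | Conflict |
| Second Grade 2 or worse on the slower rate | Silent | Stop and remove | Gap, filled by Table 9 |

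The clear conflict is therefore limited to the fourth and fifth rows. The second row is a difference in threshold, and the last is an omission.

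**How often could the conflict rows arise?** The documents give no rate of utomilumab infusion reactions by grade. Section 1.2.2 gives treatment-related adverse events, which bound the severe cases if a severe infusion reaction would have been recorded as treatment-related.

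- Patients exposed: 47 (single agent) + 40 (with rituximab) + 23 (with pembrolizumab) = 110.
- Grade 4 or 5 treatment-related events: none in the first two groups, and nothing of Grade 3 or higher in the third, so 0 of 110. With no events, the one-sided 95% upper limit is 1 − 0.05^(1/n). For n = 110 this is 1 − 0.05^(1/110) = 0.0269, or 2.7%.
- Grade 3 or higher infusion reactions: the text is explicit only for the two combination groups, 40 + 23 = 63 patients. Their only event of Grade 3 or higher was a thrombocytopenia, so 0 of 63. The limit is 1 − 0.05^(1/63) = 0.0464, or 4.6%.
- The 47 single-agent patients are left out of the second count because Section 1.2.2 describes one Grade 3 event (fatigue) without saying that it was the only one. If it was, the count is 0 of 110 and the limit 2.7%.

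These data come from other dosing and without avelumab, so they indicate rarity and do not estimate a rate for this trial. Nothing in the documents gives a utomilumab rate for Grade 2 or repeat reactions.

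**The case against.** The strongest reply is that the protocol already has the rule. Table 9 names utomilumab and covers every grade and repeats, and Section 5.2.4.3 states the tables as an obligation. Section 5.2.3.2 only grants a permission, and a permission does not displace a specific obligation. That stands, and it settles which text should prevail. It does not remove the inconsistency: no precedence is stated, and the only pointer to the tables is in Section 5.2.4.3.

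Several narrower replies also have force.

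- The stop for symptoms that persist or worsen already ends most prolonged Grade 3 infusions. A recurrence after restarting might also be read as persistence, which would leave Grade 4 and hospitalized Grade 3 reactions that improve.
- Improvement in Section 5.2.3.2 may be shorthand for Table 9's Grade 1 threshold. It can be read so, but it does not say so.
- Sections 5.2.3.1 and 5.2.3.3 do not cite Table 9 either. True, but neither contains its own rule for continuing after a reaction.

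A reader might infer more than the documents support in three ways.

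- That Section 5.2.3.2 authorizes repeated halving after repeat reactions. It says nothing on repeats, and silence does not override Table 9.
- That Table 8 independently confirms Table 9 throughout. Table 8 exempts some short-lived Grade 3 symptoms, such as fever, headache and nausea, which could be how an infusion reaction presents.
- That Arm D dose-finding is compromised, because Section 3.3 counts discontinuation for possibly related toxicity during the DLT period as a DLT. An isolated classification could turn on which text staff followed. But a Grade 3 or higher reaction would generally be caught by Section 3.3's general Grade 3 non-hematologic criterion anyway, and for a second Grade 2 reaction Table 9 is the only rule stated. The decision rules do not change.

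**Conclusion.** The inconsistency is real and minor. Section 5.2.3.2 is looser than Table 9 in one clear respect: a Grade 4 reaction, or a Grade 3 reaction that needs hospitalization or recurs, may be followed by half-rate continuation if it then improves. It is looser in one matter of degree, the threshold for restarting after Grade 2, and silent on a second Grade 2 or worse reaction. Table 9 is the better reading, so the documents do not support saying that the protocol lacks a safety rule or that it endorses rechallenge after severe reactions.

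The severe cases should be rare, given upper limits of 2.7% for Grade 4 or 5 and 4.6% for Grade 3 or higher. Those limits assume that the earlier utomilumab experience carries over to this trial's doses and to use with avelumab, and that infusion reactions were counted as treatment-related. Sample size and the planned analyses are unaffected.

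**What to change.** Replace the half-rate sentence in Section 5.2.3.2 with wording such as:

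*Manage all infusion reactions per Table 9, which governs. Half-rate continuation is allowed only for Grade 1, or for a first Grade 2 reaction that has resolved or fallen to Grade 1; Grade 3-4, or a second Grade ≥2 reaction on the slower rate, requires stopping and withdrawal from study treatment.*

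Do not restrict continuation to a first Grade 1 reaction. Table 9 sets no such limit, and adding one would create a new mismatch.

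The cost is two sentences of protocol text, with no change to sample size, visits or analysis.
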